| 
Other secondary objectives are:
 
 
• To compare both ixekizumab regimens (80 mg Q2W or 80 mg Q4W) to placebo during the 52-week period
 
   | 
 
• Proportion of patients who achieve ASAS20, ASAS40, ASAS5/6, and partial remission by ASAS criteria
 
• Change from baseline in the individual components of the ASAS criteria
 
• Change from baseline in Bath Ankylosing Spondylitis Disease Activity Index (BASDAI)
 
• Proportion of patients reaching BASDAI50
 
• Change from baseline in ASDAS
 
• Proportion of patients who experience clinically-important improvement (change of ASDAS from baseline <math>\geq 1.1</math>), major improvement (change of ASDAS from baseline <math>\geq 2.0</math>), or inactive
 
   |

| Objectives  | Endpoints   |
|---|---|
|   | 
disease (ASDAS <1.3)
 
 
• Change from baseline in the measure of CRP
 
• Change from baseline in BASFI
 
• Change from baseline in mobility                             
 
○ Bath Ankylosing Spondylitis Metrology Index (BASMI) (linear) and individual components
 
○ Chest expansion
 
○ Change from baseline in occiput to wall distance
 
 
 
• Change from baseline in MRI of the SIJ (SPARCC score)
 
• Change from baseline in SPARCC SIJ Structural Score (SSS)
 
• Change from baseline in Maastricht Ankylosing Spondylitis Enthesitis Score (MASES)
 
• Change from baseline in SPARCC Enthesitis Score
 
• The incidence and severity of peripheral arthritis by tender and swollen joint count scores of 46/44 joints
 
• Incidence rate of anterior uveitis or uveitis flares
 
• Change from baseline in the following health outcomes measures: Fatigue NRS score, ASAS-HI score, Jenkins Sleep Evaluation Questionnaire (JSEQ), Work Productivity Activity Impairment—Spondyloarthritis (WPAI-SpA) scores, SF-36 (both physical component [PCS] and mental component scores [MCS]), and Quick Inventory of Depressive Symptomatology–Self-Report (16 Items) (QIDS-SR16) score.
 
• NSAID intake (ASAS-NSAID score and % of patients taking NSAIDs)
 
 |

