##### 9.4.2.2.1. Period 2 (Blinded Treatment Dosing Period)

Unless otherwise specified, the other secondary analyses during Period 2 will be based on the ITT population.

Treatment comparisons in the proportion of patients achieving a categorical response at specified time point will be analyzed using the logistic regression model defined in Section 9.2.1. Missing data will be imputed using the NRI method described in Section 9.2.4.

For all continuous efficacy variables that are collected at repeated visits, treatment group comparisons will be analyzed using the MMRM model defined in Section 9.2.1. No imputation methods are applied to MMRM analysis. Additional analysis will be conducted using ANCOVA model defined in Section 9.2.1. Missing data will be imputed by the mBOCF method as described in Section 9.2.4.

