
Other secondary objectives are:
 
 
To compare both ixekizumab regimens (80 mg Q2W or 80 mg Q4W) to placebo during the 52-week period
 
	
 
Proportion of patients who achieve ASAS20, ASAS40, ASAS5/6, and partial remission by ASAS criteria
 
Change from baseline in the individual components of the ASAS criteria
 
Change from baseline in Bath Ankylosing Spondylitis Disease Activity Index (BASDAI)
 
Proportion of patients reaching BASDAI50
 

Objectives	Endpoints
	
 
• Change from baseline in ASDAS
 
• Proportion of patients who experience clinically-important improvement (change of ASDAS from baseline <math>\geq 1.1</math>), major improvement (change of ASDAS from baseline <math>\geq 2.0</math>), or inactive disease (ASDAS <math>< 1.3</math>), or ASDAS <math>< 2.1</math>
 
• Change from baseline in the measure of C-reactive protein (CRP)
 
• Change from baseline in Bath Ankylosing Spondylitis Functional Index (BASFI)
 
• Change from baseline in mobility                         
 
○ Bath Ankylosing Spondylitis Metrology Index (BASMI) (linear) and individual components
 
○ Chest expansion
 
○ Change from baseline in occiput to wall distance
 
 
 
• Change from baseline in MRI of the SIJ (SPARCC score)
 
• Change from baseline in SPARCC SIJ Structural Score (SSS)
 
• Change from baseline in Maastricht Ankylosing Spondylitis Enthesitis Score (MASES)
 
• Change from baseline in SPARCC Enthesitis Score
 
• The incidence and severity of peripheral arthritis by tender and swollen joint count scores of 46/44 joints
 
• Incidence rate of anterior uveitis or uveitis flares
 
• Change from baseline in the following health outcomes measures: Fatigue numeric rating scale (NRS) score, ASAS Health Index (HI) score, Jenkins Sleep Evaluation Questionnaire (JSEQ), Work Productivity Activity Impairment—Spondyloarthritis (WPAI-SpA) scores, SF-36 (both physical component [PCS] and mental component scores [MCS]), and Quick Inventory of Depressive Symptomatology–Self-Report (16 Items) (QIDS-SR16) score.
 
• Nonsteroidal anti-inflammatory drug (NSAID) intake (ASAS-NSAID score and % of patients taking NSAIDs)
 

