Measure	Variable	Analysis Method (Sections 6.1 and 6.3)	Population (Section 6.1.1)	Comparison/Time Point	Analysis Type
	TJC = 0 when patients had current or historical peripheral arthritis at baseline (similarly SJC = 0 when patients had current or historical peripheral arthritis at baseline)	Logistic regression analysis with NRI; Fisher’s exact test with NRI	ITT Population with Current or Historical Peripheral Arthritis at Baseline	IXE80Q2W & IXE80Q4W vs. placebo at Week 16 and 52 and all other postbaseline visits in Period 2	Other secondary efficacy analyses (Section 6.10.4).
Anterior uveitis	Crude and exposure-adjusted incidence rates for patients with anterior uveitis	Fisher’s exact test and Poisson regression	ITT Population	IXE80Q2W & IXE80Q4W vs. placebo during Period 2	Other secondary efficacy analyses (Section 6.10.4).
NSAID (including COX-2 inhibitor) Intake	Proportion of patients taking NSAID (including COX-2 inhibitor)	Descriptive statistics	ITT Population	At Baseline (Week 0), Weeks 16, 20, 24, 28, 32, 36, 44, 52.	Analyses on NSAID intake (Section 6.10.4.1)
	Change from baseline in ASAS-NSAID	Descriptive statistics	ITT Population who have NSAID (including COX-2 inhibitor) intake at Baseline	At Weeks 16, 20, 24, 28, 32, 36, 44, 52.	Analyses on NSAID intake (Section 6.10.4.1)

Measure	Variable	Analysis Method (Sections 6.1 and 6.3)	Population (Section 6.1.1)	Comparison/Time Point	Analysis Type
	ASAS-NSAID50	Descriptive statistics	ITT Population who have NSAID (including COX-2 inhibitor) intake at Baseline	At Weeks 16, 20, 24, 28, 32, 36, 44, 52.	Analyses on NSAID intake (Section 6.10.4.1)

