#### **6.10.4. Other Secondary Efficacy Analyses**

There will be no adjustment for multiple comparisons for other secondary efficacy analyses.

The other secondary efficacy analyses include:

- ASAS40: analyses other than primary analysis (Section 6.10.1), and additional analysis of the primary outcome (Section 6.10.3)
- ASAS20, ASAS5/6 and partial remission
- Change from baseline in individual components of the ASAS criteria (patient global, spinal pain, function [see BASFI below], inflammation [see BASDAI below], CRP [see CRP below], and spinal mobility (lateral spinal flexion) [see BASMI below])
- Change from baseline in BASDAI: analyses other than major secondary efficacy analysis, 6 individual items and inflammation (mean of Q5 and Q6 on BASDAI)
- BASDAI 50
- Change from baseline in ASDAS: analyses other than major secondary efficacy analysis (Section 6.10.2)
- ASDAS inactive disease (ASDAS<1.3)
- ASDAS disease activity states: inactive disease, low disease activity, high disease activity, very high disease activity, clinically important improvement and major improvement
- Change from baseline in CRP
- Change from baseline in BASFI
- Change from baseline in mobility (BASMI linear and individual components, chest expansion, occiput to wall distance)
- Change from baseline in SPARCC SIJ score: analyses other than major secondary efficacy analysis (Section 6.10.2)
- Change from baseline in SPARCC SIJ structural score (SSS) for each of the 4 features: fat metaplasia, bone erosion, backfill and ankyloses.

- Change from baseline in enthesitis score (MASES and SPARCC)
- Change from baseline in TJC and SJC scores
- Incidence of peripheral arthritis by TJC and SJC scores of 46/44 joints.
- Incidence rate of anterior uveitis
- Change from baseline in ASAS-NSAID score, Section [6.10.4.1](#).

Treatment comparisons of each ixekizumab treatment group and placebo at Weeks 16 and 52 and all other postbaseline visits during Period 2 for the ITT Population will be provided. For inadequate responders who were treated with biologic rescue of ixekizumab 80 mg Q2W, only data up to the time of initiation of biologic rescue of ixekizumab 80 mg Q2W will be included in these analysis.

The impact of ixekizumab starting doses will be evaluated for the selected categorical responses and mean change in selected continuous efficacy and health outcome measures at Weeks 16 and 52 and earlier time point as described in Section [6.1.2](#).

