$$100 \text{ (20 mg piroxicam score)} \times 120 \text{ (4 months)} \times 4/7 \text{ (3-5 days/ week)} / 180 \text{ (6 months)} = 38.1$$

If the patient has used 10 mg piroxicam during the remaining 2 months on 2 days a week, the NSAID score for this period is:

$$50 \text{ (10 mg piroxicam score)} \times 60 \text{ (2 months)} \times 2/7 \text{ (1-3 days/week)} / 180 \text{ (6 months)} = 4.8$$

In this example, the total score for the 6-month period is 42.9 (38.1 plus 4.8).

The ASAS-NSAID score will be summarized for the following endpoints at baseline Week 0 (when applicable) and each scheduled visit of interest, which includes the timeframe after the date of previous visit to the date of current visit:

- Change from baseline in ASAS-NSAID
- Proportion of patients with 50% decrease in ASAS-NSAID scores compared with baseline
- Proportion of patients with ASAS-NSAID score <10
- Proportion of patients with ASAS-NSAID score = 0.

In addition, proportion of patients taking NSAID at specified visit will be summarized.

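### NSAID intake is an endpoint for comparing each ixekizumab regimen with placebo, but the SAP's method table and Section 6.10.4.1 give only descriptive statistics for it, against SAP Section 6.10.4 and the protocol's default methods

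*SAP*

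**What the plan says.** Protocol Table RHBX.1 lists "NSAID intake (ASAS-NSAID score and % of patients taking NSAIDs") among the other secondary endpoints. The objective beside it is to compare both ixekizumab regimens with placebo during the 52-week period. SAP Section 4 repeats the endpoint under the same objective.

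For other secondary efficacy endpoints, Protocol Section 9.4.2.2.1 gives default methods. For categorical endpoints: "Treatment comparisons in the proportion of patients achieving a categorical response at specified time point will be analyzed using the logistic regression model", with missing data handled by NRI. Continuous efficacy variables collected at repeated visits are to be compared by MMRM, with ANCOVA and mBOCF as the additional analysis.

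SAP Section 6.10.4 lists change from baseline in ASAS-NSAID score as one of the other secondary efficacy analyses. Directly after the list it says that "Treatment comparisons of each ixekizumab treatment group and placebo at Weeks 16 and 52 and all other postbaseline visits during Period 2" will be provided for the ITT Population, and it sends the reader to Table RHBX.6.5 for methods, imputation and comparisons.

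In that table the score row reads "Change from baseline in ASAS-NSAID Descriptive statistics". The rows for the proportion taking NSAIDs and for ASAS-NSAID50 also give "Descriptive statistics". All three rows list visits; none names arms or an imputation rule. Section 6.10.4.1 speaks only of summaries: "The ASAS-NSAID score will be summarized for the following endpoints at baseline Week 0 (when applicable) and each scheduled visit of interest". It adds: "In addition, proportion of patients taking NSAID at specified visit will be summarized".

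**The concern.** The plan sets a comparative objective, and one section of the SAP promises the comparison. The table that should supply the method supplies none. A programmer who follows the table and Section 6.10.4.1 will produce percentages and means by arm, with no treatment difference, confidence interval or test for the ASAS-NSAID score, ASAS-NSAID50 or NSAID use by visit. A programmer who follows Section 6.10.4 must choose a model, which could happen after unblinding. Either way, the question of whether ixekizumab reduces NSAID need relative to placebo has no pre-specified answer. No reason for a descriptive-only analysis is given, and the SAP revision history entry for Section 6.10.4.1 mentions only the NSAID equivalence scoring.

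**Working it through.** **1. The plan's own figure.** The worked example in SAP Section 6.10.4.1 reproduces: 100 × 120 × (4/7) / 180 = 38.1; 50 × 60 × (2/7) / 180 = 4.8; total 42.9. The score is well defined. The gap is in how the arms are compared on it.

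**2. The sections side by side.**
- Protocol Table RHBX.1 and SAP Section 4: NSAID intake sits under a comparison with placebo.
- SAP Section 6.1.2.1: each ixekizumab group is compared with placebo in all Period 2 analyses.
- SAP Section 6.10.4: comparisons with placebo will be provided for a list that includes ASAS-NSAID change.
- SAP Table RHBX.6.5, three NSAID rows: descriptive statistics, no arms, no imputation. The anterior uveitis row just above names Fisher's exact test, Poisson regression and both regimens against placebo.
- SAP Section 6.10.4.1: summaries only. It adds the proportions with a score below 10 and equal to 0, which have no row in the table.

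The first three call for a comparison, and the last two specify none.

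**3. Does the test in SAP Section 6.9.2 fill the gap?** That section compares concomitant NSAID use (including COX-2 inhibitors) between arms by Fisher's exact test, in Period 2 before ixekizumab rescue, in the ITT Population. Protocol Section 9.3.3 plans a similar comparison. Under the SAP definition, a therapy that starts before first dose and continues into the period is concomitant, so a baseline user who stops at, say, Week 20 is still counted.

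The documents do not give the number of baseline users. Assume 70 to 90 per 100 in each arm. The any-use percentage then cannot fall below 70% to 90% in either arm, however many patients stop. It can rise only through new starters among the 30 to 10 per 100 who were not users. With 100 per arm, exact Fisher power is 81% for 90% v 74%. If placebo any-use were 90%, the largest possible gap would be 90 − 70 = 20, 90 − 80 = 10 or 90 − 90 = 0 points at the three baseline levels, and all of it would come from patients starting NSAIDs. The test can detect new starts; it cannot detect reduction.

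**4. Would a proper comparison be informative?** This is illustrative only, because the effect sizes are assumptions. Two-sided 0.05 Fisher power (exact enumeration), with 70, 80 and 90 baseline users per arm:
- ASAS-NSAID50 of 40% v 20%: 68%, 75%, 80%.
- ASAS-NSAID50 of 30% v 20%: 21%, 25%, 28%.

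Two-sample t-test power for change in score, same numbers per arm:
- 0.5 SD difference: 84%, 88%, 92%.
- 0.3 SD difference: 42%, 47%, 52%.

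A large effect would be detectable and a modest one would not. The estimate and interval matter more than the p-value.

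**5. Which visit.** Protocol Sections 6.8 and 6.8.1 hold NSAID doses stable through Week 16 unless a change is needed for safety. Section 6.8.2 allows changes afterwards. Week 16 therefore carries little information on reduction, and Week 52 is the natural main time point.

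**The case against.** A reader might infer that the arms are never compared on NSAID use, so that the chance of finding a difference is nil. The documents do not support that. SAP Section 6.9.2 runs a Fisher test on NSAID use before rescue, and Sections 6.10.4 and 6.1.2.1 promise comparisons with placebo. The supportable statement is that no method is specified for the score, for ASAS-NSAID50 or for use by visit.

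A reader might also infer from the blank imputation entries that the Week 52 figures would describe only patients who were never rescued. That is not established either. Section 6.3.1 applies NRI to categorical efficacy variables and counts rescued patients as nonresponders. Section 6.3.2 applies mBOCF to continuous variables in the other secondary objectives. These general rules may already cover the NSAID rows, although the rows do not say so.

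The conflict with the protocol is softer than the conflict within the SAP. Protocol Section 9.4.2.2 leaves the details to the SAP, and Section 9.2 allows changes that do not alter a principal feature without an amendment, with the justification given in the study report. It can also be argued whether taking an NSAID at a visit counts as a categorical response.

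The best defence on substance is that, after Week 16, NSAID changes are partly the investigator's response to inadequate control, so intake mixes drug effect with management. That could justify describing rather than testing, but the SAP does not say it. A blinded randomised comparison of intake would still be valid as an effect on NSAID use under the trial's rules.

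**Conclusion.** The point holds in this form: SAP Section 6.10.4 contradicts Table RHBX.6.5 and Section 6.10.4.1 on whether NSAID outcomes are compared with placebo. As the table stands, a stated comparative objective goes unanswered for the ASAS-NSAID score, ASAS-NSAID50 and NSAID use by visit. The inconsistency is read directly from the text and rests on no numerical assumption; only the any-use floor and the power figures do.

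The size is small. Three table rows are affected, for one other secondary endpoint outside the multiplicity scheme. No primary or major secondary conclusion changes. It is worth correcting but not essential.

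**What to change.** In Table RHBX.6.5 and Section 6.10.4.1, compare Q2W and Q4W each with placebo, with Week 52 as the main time point:
- Change in ASAS-NSAID score, in baseline NSAID users: MMRM as in Section 6.1.2.1, with ANCOVA with mBOCF as secondary.
- ASAS-NSAID50, in baseline users: logistic regression with treatment, geographic region and screening MRI/CRP status, with NRI, and Fisher's exact test as secondary. If wanted, treat scores below 10 and equal to 0 the same way. Table RHBX.6.4 sets the score to 0 when no NSAID is used, so the last of these addresses stopping NSAIDs.
- State that the rescue handling in Sections 6.3.1 and 6.3.2 applies to these rows.
- Report differences with 95% confidence intervals and no multiplicity adjustment.
- If the by-visit percentage taking NSAIDs stays descriptive, say so in Section 6.10.4 and give the reason.

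The cost is SAP wording and a few outputs on data already collected; no protocol amendment is needed. At Week 52 the two core endpoints add 2 endpoints × 2 methods × 2 regimens = 8 unadjusted p-values, or 16 if the two optional cut-offs are included. Running every method at all eight listed visits would multiply that by eight, which is a reason to keep the focus on Week 52.

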### 6.10.5. Sensitivity Analyses

#### 6.10.5.1. pMI

ASAS40 and mean change in ASDAS at Weeks 16 and 52 will be analyzed based on the ITT Population using the pMI method, as described in Section 6.3.4. Analyses for ASAS40 will be based on the logistic regression analysis with treatment, geographic region, and screening MRI/CRP status in the model (Section 6.1.2). Analysis for mean change in ASDAS will be based on MMRM analysis. The model will include treatment, geographic region, screening

MRI/CRP status, baseline value, visit, baseline value-by-visit, and treatment-by-visit interaction as fixed factors (Section 6.1.2).

#### **6.10.5.2. Tipping Point Analysis**

ASAS40 and mean change in ASDAS at Weeks 16 and 52 will be analyzed based on the ITT Population using the tipping point method (Section 6.3.5).

### **6.10.6. Exploratory Analyses**

#### **6.10.6.1. Exploratory Analyses Post Biologic Rescue for Inadequate Responders**

For inadequate responders who initiated biologic rescue of ixekizumab 80 mg Q2W, summary statistics will be provided for categorical measures (ASAS40/20, BASDAI50, ASDAS <2.1, ASDAS clinical important improvement and major improvement) and continuous measures (CRP, BASFI, BASDAI, SF-36 PCS) to describe the treatment response post biologic rescue. For patients who further initiated other biologic rescues (such as TNF-i), a listing of ASAS40 and its domains, BASDAI score and CRP value will be produced. The length of exposure on initially randomized therapy, and biologic rescue of ixekizumab 80 mg Q2W will be summarized separately for the IR Population.

#### **6.10.6.2. Use of Rescue Therapy During Period 2 for ITT Population**

The time to initiation of biologic rescue of ixekizumab 80 mg Q2W (in weeks) will be summarized by treatment group and graphically presented using Kaplan-Meier techniques for Period 2. The time to initiation of biologic rescue of ixekizumab 80 mg Q2W will be calculated as:

$$\frac{(\text{Date of initiating biologic rescue ixekizumab 80 mg Q2W in Period 2} - \text{Date of first dose in Period 2} + 1) / 7}{}$$

Patients who did not initiate biologic rescue of ixekizumab 80 mg Q2W will be censored at the date of completion (that is, the date of the last scheduled visit in the period) or discontinuation. Patients without a date of Period 2 completion or discontinuation will be censored at the latest non-missing date out of the following dates: date of last dose on the initially assigned treatment and date of last attended visit in Period 2 (scheduled or unscheduled) (Analysis population: ITT).

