## 4. Study Design

### 4.1. Overview of Study Design

Study IIF-MC-RHBX (RHBX) is a Phase 3, multicenter, randomized, double-blind, placebo-controlled, parallel-group, outpatient study examining the efficacy and safety of 2 ixekizumab treatment regimens (80 mg Q2W and 80 mg Q4W SC) as compared to placebo SC in patients with active nonrad-axSpA who are bDMARD-naïve, during a double-blind, 52-week treatment period (Period 2).

[Figure RHBX.1](#) illustrates the study design. Within the active treatment groups, half the patients will be given a 160-mg starting dose and the other half will be given an 80-mg starting dose. All treatment groups and administration of the investigational product are described in [Section 6.1](#), and the Study Drug Administration Log is described in [Section 6.2.1](#).

All procedures to be conducted during the study, including timing of all procedures, are indicated in the Schedule of Activities ([Appendix 2](#)). Selected study procedures are to be performed before administration of the investigational product, as applicable.

For each patient, x-rays and magnetic resonance imaging (MRIs) will be collected according to [Section 8.1.2.21.1](#) and the Schedule of Activities ([Appendix 2](#)).

[Appendix 3](#) lists the specific laboratory tests that will be performed for this study. At or after Week 16, patients who are deemed inadequate responders may receive rescue therapies as described in [Section 6.1.1](#). Patients discontinuing study treatment after Week 16 are to remain in the study and follow the regular visit schedule.

[figure not shown]
Patients who have taken at least 1 study dose and who discontinue study treatment prior to Week 16 or study participation (regardless of timing) are to complete an early termination visit (ETV) and enter into post-study follow-up for at least 12 weeks after the ETV date or the last regularly scheduled visit. Patients whose ETV or last regularly scheduled visit is longer than 12 weeks after their last investigational study medication dose are not required to enter into the Post-Study Follow-Up Period (Period 3). For the management of patient safety, patients are to be monitored through the Post-Study Follow-Up Period as indicated on the Schedule of Activities ([Appendix 2](#)).

Patients who complete Study RHBX may be eligible to enroll into a long-term extension study (Study IIF-MC-RHBY [RHBY]) for up to 2 additional years.

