## 6. Treatment

### 6.1. Treatments Administered

The Blinded Treatment Dosing Period (Period 2) involves a comparison of ixekizumab at 2 treatment regimens (80 mg Q2W and 80 mg Q4W) with placebo treatment. Each ixekizumab treatment regimen will include patients receiving an 80-mg or a 160-mg starting dose; patients will be randomized to a starting dose at a 1:1 ratio. All doses are administered via SC injection. [Table RHBX.2](#) shows the treatment regimens.

At baseline (Week 0), all patients will be randomized to a treatment group and receive 2 injections. Patients assigned to an ixekizumab treatment regimen with a 160-mg ixekizumab starting dose will receive 160-mg of ixekizumab as 2 SC injections (80 mg per SC injection). Patients assigned to an ixekizumab treatment regimen with an 80-mg starting dose will receive 80 mg of ixekizumab as 1 SC injection and 1 SC injection of placebo. Patients assigned to the placebo treatment group will receive 2 SC injections of placebo. After Week 0 and through Week 50, all patients will receive 1 injection every 2 weeks. Details of the patient treatment regimens are provided in [Table RHBX.2](#).

Beginning at Week 16 and up to Week 44, any patient, regardless of their original treatment group, may be identified by an investigator based on clinical judgment as an inadequate responder. At such time, changes in background therapy and/or addition of biologic rescue therapy (ixekizumab 80 mg Q2W) can be made at the discretion of the investigator, while remaining blinded to the original randomization treatment assignment. Changes in ongoing medications at that time can include changes in dose of NSAIDs or nonbiological disease-modifying antirheumatic drugs (DMARDs), including the introduction of new medications. The investigator may also decide to use biologic rescue of ixekizumab 80 mg Q2W with an 80-mg starting dose, which is a blinded decision as to whether the patient will be initiating ixekizumab, increasing the dose, or remaining on the same treatment regimen.

Investigators who believe a patient needs rescue ixekizumab 80 mg Q2W treatment will indicate such via interactive web-response system (IWRS), and these patients will receive ixekizumab 80 mg Q2W with an 80-mg starting dose. This option specifically means the following:

- Placebo inadequate responders will switch to ixekizumab 80 mg Q2W.
- Ixekizumab 80 mg Q4W inadequate responders will switch to ixekizumab 80 mg Q2W.

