**Observation:** For safety monitoring patients are to remain under observation for at least 1 hour after dosing at Week 0 (Visit 2) and at any visit on or after Week 16 in which a patient receives the initial injection of ixekizumab as rescue therapy. This initial injection of rescue ixekizumab will be administered by the patient or caregiver at the clinical site to allow for observation for any AEs and for collection of postinjection blood pressure (BP) and pulse measurements approximately 1 hour after administration of the investigational product (Section 8.4.2 and Appendix 2).

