## 7. Discontinuation Criteria

The reason for and date of discontinuation from study treatment (investigational product) and reason for and date of discontinuation from study participation will be collected for all randomized patients.

Patients who have taken at least 1 study dose and who discontinue study treatment prior to Week 16 or study participation (regardless of timing) are to complete an ETV and enter into post-study follow-up for at least 12 weeks after the ETV date or the last regularly scheduled visit. Patients whose ETV or last regularly scheduled visit is longer than 12 weeks after their last investigational study medication dose are not required to enter into the Post-Study Follow-Up Period. Patients who complete the study through Week 52 and who are not entering into Study RHBX are to enter into the Post-Study Follow-Up Period (Period 3) as shown in the Schedule of Activities ([Appendix 2](#)).

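### The exploratory Kaplan-Meier curve of time to ixekizumab rescue censors patients at an undefined "discontinuation" that can rule out rescue, so it will tend to overstate the share of each arm rescued

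*SAP*

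**What the plan says.** SAP 6.10.6.2, under the exploratory analyses, has time from first dose to rescue summarised by treatment group and "graphically presented using Kaplan-Meier techniques for Period 2" in the ITT population. Patients who did not start rescue "will be censored at the date of completion (that is, the date of the last scheduled visit in the period) or discontinuation". A fallback rule follows: "Patients without a date of Period 2 completion or discontinuation will be censored" at the later of last dose on assigned treatment and last attended Period 2 visit. No competing event is named, no test is planned, and "discontinuation" is not defined.

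The protocol passages that decide who can be rescued are these:

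- **Rescue window (6.1):** "Beginning at Week 16 and up to Week 44, any patient, regardless of their original treatment group, may be identified by an investigator" as an inadequate responder. The window has a start and an end.
- **Stopping before Week 16 (7, also 4.1):** patients who stop treatment this early "are to complete an ETV and enter into post-study follow-up for at least 12 weeks after the ETV date". They are out of Period 2 before the window opens.
- **Stopping after Week 16 (4.1):** patients stay in the study on the regular visit schedule, off study treatment.
- **What study treatment is (7):** the protocol equates it with investigational product: "discontinuation from study treatment (investigational product)".
- **What rescue is (6.1.1):** the first rescue injection is given on site, with blood pressure and "pulse measurements approximately 1 hour after administration of the investigational product". Rescue ixekizumab is therefore itself investigational product.

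**The concern.** Kaplan-Meier censoring assumes that a censored patient could still have the event later, at the same rate as those who remain at risk. A patient who stopped treatment before Week 16 cannot be rescued at all. A patient who permanently stopped investigational product later also seems unable to be. Kaplan-Meier nevertheless shares their weight among those still on treatment. The result describes rescue in a trial without discontinuation, and the SAP does not label it that way.

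Rescue by arm is useful context. A patient who starts ixekizumab rescue becomes a Week 52 nonresponder (SAP 6.3.1), and later data are dropped from the MMRM and from the ITT and Safety analyses (SAP 6.10.2, 6.1.2.1). A reader who takes the end of the curve as the share rescued would get too high a figure, and one that differs without explanation from the percentages in SAP 6.6. If discontinuation differs between arms, the apparent difference in rescue is distorted as well.

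**Working it through.** The documents state no rescue rate, discontinuation rate or time-to-rescue figure, so there is nothing of the plan's to reproduce. The rates below are assumptions chosen to show a range.

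**Inputs from the documents.** 100 patients per arm (SAP 5.2). Rescue is possible at the visits marked for treatment modification in Protocol Appendix 2: Weeks 16, 20, 24, 28, 32, 36 and 44, which is 7 occasions.

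**Assumed.** Rescues are spread evenly over the 7 visits. Stops after Week 16 are spread evenly over the 6 gaps between them.

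**Formulas.** With d rescued out of n at risk at each visit, 1-KM = 1 − Π(1 − d/n). With discontinuation as a competing event and complete follow-up, the cumulative incidence at Week 52 is simply rescued ÷ randomised.

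**Period 2 reading** (only leaving Period 2 is censored; treatment stoppers after Week 16 stay in the risk set). With 5% stopping before Week 16, 95 are at risk when rescue opens. If 40 are rescued, 1-KM = 40/95 = 42.1%, against 40/100 = 40.0%. With 10% stopping early it is 40/90 = 44.4%. These figures assume that nobody leaves the study altogether between Weeks 16 and 44. Any who did would be censored too and would push the figure up.

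**Treatment reading** (stopping study treatment is censored). With 40 rescued, d = 40/7 = 5.714 per visit.

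- *2% before and 3% after.* The first risk set is 98 and each later one is smaller by 5.714 + 3/6 = 6.214, giving 98, 91.8, 85.6, 79.4, 73.1, 66.9, 60.7. The product of (1 − 5.714/n) is 0.584, so 1-KM = 41.6%.
- *10% before and 10% after.* The first risk set is 90 and each later one is smaller by 5.714 + 10/6 = 7.381, giving 90, 82.6, 75.2, 67.9, 60.5, 53.1, 45.7. The product is 0.522, so 1-KM = 47.8%.

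Results with 40% truly rescued:

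| Stop before / after Week 16 | 1-KM, treatment reading | 1-KM, Period 2 reading |
|---|---|---|
| 0% / 0% | 40.0% | 40.0% |
| 2% / 3% | 41.6% | 40.8% |
| 5% / 5% | 43.5% | 42.1% |
| 5% / 10% | 45.1% | 42.1% |
| 10% / 10% | 47.8% | 44.4% |

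At 20% truly rescued, the treatment reading gives 20.8% (2%/3%) to 23.7% (10%/10%). At 60% it gives 62.5% to 72.7%. Over the non-zero scenarios the excess therefore runs from 0.8 to 12.7 points on the treatment reading.

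**Scale.** The binomial standard error of 40% in 100 patients is √(0.4 × 0.6/100) = 4.9 points. The excess of 1.6 to 7.8 points is thus about 0.3 to 1.6 standard errors.

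**Between arms.** Take two arms with the same 40% rescued, one with 5% and one with 10% stopping before Week 16. On the Period 2 reading they would show 42.1% and 44.4%, an apparent gap of 2.3 points where none exists.

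**The case against.** The strongest reply is that the SAP never says this curve estimates the proportion of randomised patients rescued. Censoring those who leave gives a cause-specific description of rescue, which is a legitimate target. The proportion rescued is already planned with the right denominator: SAP 6.6 reports, by arm in the ITT population, patients completing Week 52 on ixekizumab rescue and patients leaving assigned treatment as inadequate responders. SAP 6.6 also allows a Kaplan-Meier curve of leaving assigned treatment in which rescue counts as an event. That composite is closer to what makes a patient a Week 52 nonresponder. Nothing inferential depends on the curve in 6.10.6.2.

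All of that stands, and it keeps the point small. It does not remove it: the curve is not labelled cause-specific, and it will sit beside crude percentages that it does not match.

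Three stronger readings are tempting, and the documents do not support them:

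- **That this curve is how the Week 52 result will be judged.** No section gives it that role.
- **That a patient who stops treatment after Week 16 is expressly barred from rescue.** No general sentence says so. It follows from rescue being investigational product and from the title of Protocol 7.1.1 (permanent discontinuation). Further dosing is ruled out in so many words only for particular cases, such as certain hypersensitivity reactions (Protocol 6.6.1) and pregnancy (Appendix 2). On the Period 2 reading these patients are not censored when they stop, so they add no bias.
- **That every arm is biased whatever happens.** The excess is zero if nobody discontinues before the last rescue.

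**Conclusion.** The point holds as a limited one. Under either reading of "discontinuation", patients who stop treatment before Week 16 are censored before rescue is available, so 1-KM exceeds the share rescued whenever there are such patients and any rescues. The treatment reading adds the later stoppers and enlarges the excess.

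The size rests wholly on assumed rates and an even spread of events. At 40% truly rescued the excess is 1.6 to 7.8 points on the treatment reading, and 2.1 points on the Period 2 reading with 5% stopping early. The direction is always upward, and more so in an arm with more discontinuation. Primary and secondary inference is untouched. This is a cheap improvement to one exploratory display, together with an ambiguity in the censoring rule that needs settling in any case.

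**What to change.** In SAP 6.10.6.2:

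1. Define discontinuation as permanent discontinuation of study treatment, for any reason, before rescue.
2. Treat it as a competing event and report the Aalen-Johansen cumulative incidence of rescue by arm with 95% CI. With complete follow-up the Week 52 value equals the crude share rescued.
3. Censor patients who complete Period 2 on assigned treatment. Keep the existing last-dose/last-visit rule for patients with no completion or discontinuation date, so that nobody is left unclassified.
4. If a Kaplan-Meier curve is kept, label it cause-specific and state that it is not the proportion rescued.

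The cost is SAP wording and one event code in the programming. No new data are needed. The downside is one more event category to explain.
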